	15 1	APPENDIX I SHORT FORM 36 (SF-36) OUESTIONNAIRE	FREOR! BOOKMARK NOT DEFINED

LIST OF ABBREVIATIONS

AE Adverse Event/Adverse Experience

CFR Code of Federal Regulations

CRF Case Report Form DAPA Dapagliflozin

DEXA
Dual Energy X-ray Absorptiometry
DSMP
Data and Safety Monitoring Plan
FDA
Food and Drug Administration

GCP Good Clinical Practice

HFpEF Heart Failure with Preserved Ejection Fraction
HFrEF Heart Failure with Reduced Ejection Fraction
HIPAA Health Insurance Portability and Accountability Act

IB Investigator's Brochure

IND Investigational New Drug Application

IRB Institutional Review Board NYHA New York Heart Association

PCWP Pulmonary Capillary Wedge Pressure

PHI Protected Health Information

PI Principal Investigator

SAE Serious Adverse Event/Serious Adverse Experience

SF-36 Short Form 36 Questionnaire

Study Summary

Title	Evaluation of the Cardiac and Metabolic Effects of Dapagliflozin in Heart Failure with preserved Ejection Fraction (CAMEO-DAPA): A Phase II, Prospective, Double-Blind Study				
Running Title	CAMEO-DAPA				
Protocol Number	20-005646				
Phase	Phase II				
Methodology	Randomized, double blind placebo control				
Overall Study Duration	24 months				
Subject Participation Duration	Approximately 7 months				
Single or Multi-Site	Single				
Objectives	To determine whether treatment with DAPA for 6 months will improve pulmonary capillary wedge pressure (PCWP) at rest and during exercise in HFpEF and improve cardiac metabolism.				
Number of Subjects	Up to 41 Subjects fully completing trial, up to 46 accrual, to account for dropouts				
Diagnosis and Main Inclusion Criteria	HFpEF subjects with obesity defined by clinical symptoms of HF: Dyspnea (NYHA II-IV without cardiac or ischemia explanation), EF ≥ 50%				
Study Product, Dose, Route, Regimen	Dapagliflozin (DAPA) 10 mg once daily versus matching placebo				
Duration of Administration	6 months				
Reference therapy	Placebo				
Statistical Methodology	The principal comparisons will be a comparison of pulmonary capillary wedge pressure incorporating values measured at rest and during exercise using mixed effects model analysis of covariance.				

1 Introduction

This document is a protocol for a human research study. This study will be carried out in accordance with the applicable United States government regulations and Mayo Clinic research policies and procedures.

1.1 Background

Over 70% of individuals above the age of 65 years with heart failure (HF) have preserved ejection fraction (HFpEF). There is currently no proven treatment that improves symptoms or outcome in this population. The vast majority (75%) of patients with HFpEF are obese. Inflammation and metabolic stress secondary to excess body mass are strongly implicated in the pathophysiology of the obese phenotype of HFpEF, leading to alterations in cardiac function that cause abnormal hemodynamics, which then cause symptoms, morbidity and increased mortality.

Despite these signals from various studies, predominantly in animal models, the mechanisms by which SLGT2 inhibitors improve outcome in HF, or whether they improve clinical status in HFpEF, remain unclear. As such, characterization of the mechanisms by which dapagliflozin affects cardiac function and metabolism remains a critical unmet need. The most likely mechanisms involve improvements in hemodynamics that drive symptoms (through improvements in cardiac function and reduction in plasma volume) and improvements in myocardial metabolism, specifically alterations in the uptake and utilization of free fatty acids (FFA) vs other substrates.

The gold standard to assess each of these components is through invasive hemodynamic assessment, simultaneous echocardiography, and transcardiac blood sampling (arterial and coronary sinus), all performed at rest and during supine exercise (where symptoms develop in HFpEF). This study will test the effects of treatment with dapagliflozin for 6 months on cardiac hemodynamics, structure, function and metabolism using these methods, as compared placebo.

1.2 Investigational Agent

Dapagliflozin 10 mg tablet or matching placebo.

1.3 Clinical Data to Date

SGLT2 inhibitors such as dapagliflozin have been shown to reduce incident HF events.⁷⁻⁹ SGLT2 inhibitors are known to reduce body weight, ventricular mass, enhance insulin sensitivity, reduce plasma volume expansion and blood pressure, and improve renal outcomes.¹⁰⁻¹⁵ Each of these abnormalities has been shown to play a pivotal role in patients with the obese phenotype of HFpEF.^{5, 6, 16}

People with obesity display increased free fatty acid (FFA) uptake, which is associated with reduced myocardial efficiency.¹⁷ Treatment with DAPA may favorably alter myocardial substrate utilization by decreasing reliance on FFA and switch to alternative sources such as glucose oxidation or utilization of ketone bodies.^{18, 19}

Dapagliflozin has been shown in a large placebo controlled trial (DAPA-HF) to improve the combined primary endpoint of HF hospitalization or cardiovascular mortality in patients with HF and reduced ejection fraction (HFrEF, defined by EF<40%). Patients randomized to dapagliflozin had a statistically significant 26% reduction in the primary outcome, with a 30% reduction in HF hospitalization, 18% reduction in cardiovascular death, and a 17% reduction in all-cause mortality in patients receiving dapagliflozin. Importantly, the beneficial effects were similar in patients with and without diabetes. The frequency of adverse events related to volume depletion, renal dysfunction, and hypoglycemia did not differ between patients randomized to dapagliflozin or placebo. ²⁰

More recently, a second pivotal trial has evaluated a related SGLT2 inhibitor, empagliflozin, in the EMPEROR-Reduced trial.²¹ In this study, 3730 patients with HFrEF were treated with empagliflozin (10 mg once daily) or placebo. Consistent with the DAPA-HF trial, treatment with the SGLT2 inhibitor empagliflozin was associated with a 25% reduction in the primary outcome of cardiovascular death or hospitalization for worsening heart failure. Efficacy and safety were similar in patients with and without diabetes mellitus. Total hospitalizations were HF were reduced by 30%, and there was a significant reduction in the annual rate of decline in the estimated glomerular filtration rate.

These data have led to a new indication from the FDA to use dapagliflozin as a treatment for patients with HFrEF. While the data from DAPA-HF in HFrEF are supportive of a potential benefit in HFpEF, it is well-known that treatments that are effective in HFrEF are often not effective in HFpEF due to multiple fundamental pathophysiologic differences between the two HF phenotypes. ²² Furthermore, the potential mechanisms of effect on hemodynamic abnormalities and cardiac metabolism (in any type of HF) remain unclear, forming the basis for the present study.

1.4 Dose Rationale

This study will test the same 10 mg dose of dapagliflozin (once daily) that was shown to be safe and effective in the DAPA-HF trial.²⁰

1.5 Risks and Benefits

Dapagliflozin has been well-tolerated in patients with HFrEF in both the DAPA-HF trial²⁰ and the EMPEROR-Reduced trials.²¹ Risks reported across all studies include genital and urinary tract infections, and diabetic ketoacidosis. The frequency of adverse events related to volume depletion, renal dysfunction, and hypoglycemia did not differ between patients randomized to dapagliflozin or placebo.^{20, 21} A recent meta-analysis combining results from both DAPA-HF and EMPEROR-Reduced (n=8474) has confirmed an excellent safety profile, with lower rate of serious adverse events among patients randomized to active therapy in both trials, as shown in the Table below from Zannad et al.²³

The potential benefits from dapagliflozin include an improvement in symptoms of dyspnea and fatigue, increase in exercise capacity, improved quality of life, reduction in the risk of HF hospitalization, and reduction in the risk of death. In the meta-analysis combining the results from both DAPA-HF and EMPEROR-Reduced, there was an

estimated 13% reduction in all-cause death, 14% reduction in cardiovascular death, 26% relative reduction in the combined risk of cardiovascular death or first hospitalization for heart failure, and 25% decrease in the composite of recurrent hospitalizations for heart failure or cardiovascular death.²³ Benefits were consistent across all subgroups based on age, sex, diabetes, treatment with angiotensin-neprilysin antagonists, and at different values of baseline kidney function.

The table below presents the summary safety data for DAPA-HF and EMPEROR-Reduced, taken from Zannad et al. Lancet, 2020.²³

	EMPEROR-Reduced		DAPA-HF	DAPA-HF	
	Empagliflozin (n=1863)	Placebo (n=1867)	Dapagliflozin (n=2373)	Placebo (n=2371)	
Serious adverse events	772 (41-4%)	896 (48-1%)	846 (35.7%)	951(40-2%)	
Any renal adverse event	175 (9-4%)	192 (10-3%)	141 (6.0%)	158 (6.7%)	
Volume depletion	197 (10-6%)	184 (9.9%)	170 (7-2%)	153 (6-5%)	
Ketoacidosis	0	0	3 (0.1%)	0	
Severe hypoglycaemic events	6 (0-3%)	7 (0.4%)	4 (0-2%)	4 (0.2%)	
Bone fractures	45 (2.4%)	42 (2.3%)	48 (2.0%)	47 (2.0%)	
Lower limb amputation	13 (0.7%)	10 (0.5%)	13 (0.5%)	12 (0.5%)	
Fournier's Gangrene	1 (0.1%)	0	0	1 (0.1%)	

Given the strong evidence of both safety and efficacy in a related form of heart failure, along with the fact that dapagliflozin is FDA approved for both HFrEF and diabetes, the risk-benefit ratio very much favors benefits in the present study testing DAPA in patients with heart failure and preserved EF.

2 Study Objectives

Primary Objective

To determine whether treatment with DAPA for 6 months will improve pulmonary capillary wedge pressure (PCWP) during exercise in HFpEF.

Secondary Objectives

- 1. To determine whether treatment with DAPA for 6 months can improve myocardial metabolism and substrate utilization, shifting from high uptake of free fatty acids to favor glucose utilization.
- 2. To determine whether treatment with DAPA for 6 months will improve other hemodynamic markers of HF severity (at rest and with exercise) in HFpEF.
- 3. To determine whether treatment with DAPA for 6 months can improve ventricular function and functional reserve as assessed by tissue Doppler echocardiography and strain imaging.
- 4. To determine whether treatment with DAPA for 6 months can reduce plasma volume assessed by labelled albumin indicator dilution technique.

Page 8 of 34

Principal Investigator: [name]

5. To determine whether treatment with DAPA for 6 months can improve exercise capacity and quality of life in HFpEF, and explore how these clinical changes relate to changes in hemodynamics, cardiac function, and cardiac metabolism.

3 Study Design

3.1 General Description

This is a mechanistic phase II placebo-controlled trial designed to determine whether treatment with dapagliflozin for 6 months will improve exercise hemodynamics, cardiac metabolism, and clinically relevant endpoints in patients with HFpEF.

Brief Synopsis of Methods:

- 1) Enroll subjects with HFpEF. Some patients will have previously been identified and some will have be referred to the catheterization lab for evaluation of dyspnea and suspected HFpEF. The latter patients will only qualify for randomization if they meet hemodynamic entry criteria for HFpEF (PCWP of ≥25 mmHg with exercise).
- 2) Safety lab sampling (complete blood count, creatinine, blood urea nitrogen, sodium, potassium, aspartate aminotransferase, alanine aminotransferase, total, direct and indirect bilirubin) hs-CRP, HgA1c, NTproBNP will be performed. Values may be used up to a week prior to study if the same bloods have already been drawn.
- In the preparation area, an IV cannula will be inserted in a forearm vein for initiation of isotope infusion ([U-13C] palmitate), allowing for attainment of steady-state prior to transfer to the catheterization laboratory (~60 min). Isotope infusions will be continued until blood sampling studies have been completed.
- 4) Assess hemodynamics at rest and during exercise using gold standard invasive techniques in patients with HFpEF. Venous, arterial and coronary sinus blood samples obtained at rest and during exercise. Focused echocardiography examination with measurement of LV and RV tissue Doppler echocardiography and cardiac volumes will be performed. This will conclude the invasive catheterization visit. The patient will be monitored per standard clinical protocols following right heart catheterization and discharged the same day.
- At a separate visit following cardiac catheterization, but prior to receipt of study drug, participants will have a QOL assessment, dual energy X-ray absorptiometry (DEXA), and measurement of plasma volume using the labelled albumin indicator dilution technique. Study coordinator will review patient preferences regarding contact during the study including video teleconference (preferred) or phone call.
- Patients will be randomized in a double-blind fashion to dapagliflozin 10 mg once daily or matching placebo. Study drug dispensed by research pharmacy.
- Telephone visits will be conducted at 2 days, 1 week, 2 weeks, and then every 4 weeks thereafter, for a total of 24 weeks. One week after visit 4, there will be an additional telephone visit for safety after patient is no longer on study drug. All phone visits will have a window of +/- 3 days. Participants will be contacted by phone or through videoconference visits (based upon patient preference) to evaluate for AEs/SAEs, and encourage compliance with the study medication. Adverse events will be determined using a general approach, asking participants if there have been any changes to their overall health since the prior visit, including any unplanned hospital

Page 9 of 34

- or clinic visits. At 2 weeks, as part of standard of care, patients will undergo laboratory draw from complete blood count, electrolytes and renal function at their local lab, with results reviewed by the study teamIf needed, a physician on the trial can put in a referral order for the lab work.
- At the conclusion the 24 week treatment period, participants will return to complete the same invasive hemodynamic assessments and noninvasive assessments as described in steps (1) through (5) above (2 visits). Patient must remain on study drug through Visit 4, and may be on drug up to 7 days after the 24 week mark.
- 9) A follow up telephone/videoconference visit will be scheduled 1 week after completion of the trial to evaluate for AEs/SAEs following completion. This will have a window of +/- 3 days.

3.3 Duration of Participation

Subjects will participate in this study for up to 28 weeks.

3.4 Primary Study Endpoints

The primary endpoint will be the PCWP incorporating values at rest, with feet elevated, and at 20 Watts exercise after treatment with study drug for 6 months relative to the respective PCWP values at each stage in the initial assessment prior to study drug. This will be analyzed using a mixed model with repeated measures (MMRM).

3.5 Secondary Study Endpoints

Secondary exploratory endpoints will include:

- 1. Trans-cardiac uptake of free fatty acids (FFA), glucose, and ketone bodies uptake relative to O₂, as determined using arterial and coronary sinus blood sampling, at rest and with exercise
- 2. Changes in resting PCWP after study drug as well as rest and exercise changes in right atrial pressure and pulmonary artery pressures, rest and exercise cardiac output, and other derived hemodynamic indices.
- 3. Rest and exercise tissue Doppler diastolic (e') and systolic function (s'), LV global longitudinal strain at rest and with exercise.
- 4. Peak oxygen consumption (VO₂) during exercise, along with related cardiopulmonary indices.
- 5. Plasma volume and blood volume and quality of life (QOL) using SF-36.
- 6. Body composition including fat mass and fat free mass by DEXA scan

3.6 Primary Safety Endpoints

Safety endpoints of special interest will include symptoms suggestive of volume depletion or genitourinary infections, and laboratory abnormalities including renal function. These adverse events were not more common that placebo in DAPA-HF and will be therefore

ascertained remotely via telephone/video-teleconference for patient convenience and reduce travel burden.

3.7 Identification of Source Data

Study outcome data will be captured on electronic or paper case report forms and entered into REDCap database for subsequent analysis.

Page 11 of 34

4 Subject Selection Enrollment and Withdrawal

4.1 Inclusion Criteria

Subjects are eligible to be randomized in the study only if all of the following inclusion criteria and none of the exclusion criteria apply:

- 1. Signed informed consent prior to any study specific procedures
- 2. Male or female subject
- 3. Age ≥ 18
- 4. Symptoms of dyspnea (NYHA II-III) with no non-cardiac or ischemia explanation
- 5. EF >50%
- 6. Elevated pulmonary capillary wedge pressure (PCWP) during exercise (≥25 mmHg) ascertained at Visit 1. Patients that have consented to study procedures but do not meet this invasive criterion will be considered as screen failures and will not be randomized.

4.2 Exclusion Criteria

- 1. Type I diabetes
- 2. Type II diabetes with poor control (HgbA1c≥10%)
- 3. Recent hospitalization (<30 days) or revascularization (<90 days)
- 4. Primary cardiomyopathy (such as amyloid)
- 5. Constrictive pericarditis
- 6. Dyspnea due to primary lung disease or myocardial ischemia in the opinion of the investigator
- 7. Severe anemia (hemoglobin <9 gm/dl)
- 8. Significant left-sided valvular heart disease (>moderate stenosis, >moderate regurgitation)
- 9. Severe kidney disease (estimated GFR<30) or liver disease
- 10. Women of child bearing potential not willing to use a medically accepted method of contraception OR who are currently pregnant (confirmed with positive pregnancy test) or breast feeding.
- 11. History of serious hypersensitivity reaction to dapagliflozin
- 12. Subjects on dialysis
- 13. Subjects with severe hepatic impairment (Child-Pugh class C)
- 14. Currently taking Empagliflozin or Canagliflozin

4.3 Subject Recruitment, Enrollment and Screening

Eligible patients will be identified from screening of the patients listed for exercise right heart catheterization as well as patients with known HFpEF at the Mayo Clinic in Rochester, Minnesota.

4.4 Early Withdrawal of Subjects

4.4.1 When and How to Withdraw Subjects

Development of any condition that requires study withdrawal related to safety, disease progression, subject decision or failure to adhere to protocol requirements could qualify as reason to withdraw from the study.

Page 12 of 34

4.4.2 Data Collection and Follow-up for Withdrawn Subjects

Subjects withdrawing from the study will be contacted 2 weeks following study drug administration to collect any adverse events. Participants that withdraw may be replaced to allow for achievement of target enrollment.

5 Study Drug

5.1 Description

Dapagliflozin is a highly potent, selective, and reversible inhibitor of SGLT2 that improves glycemic control in patients with diabetes mellitus and provides cardio-renal benefits in patients with T2DM and without diabetes. Dapagliflozin is orally available and requires once-daily dosing.

Dapagliflozin is currently approved in 100 countries for the treatment of T2DM as an adjunct to diet and exercise and is also indicated for the treatment of HFrEF.

Dapagliflozin film-coated tablets used in clinical studies are available in strengths of 2.5, 5, and 10 mg. The tablets contain dapagliflozin propanediol (BMS-512148) drug substance, microcrystalline cellulose, anhydrous lactose, crospovidone, silicon dioxide, magnesium stearate, and coating material (Opadry® II). The tablets are supplied in HDPE bottles. The chemical composition is C21H25ClO6•C3H8O2•H2O, Formula weight 502.98, Molecular weight 408.87 (dapagliflozin), Appearance is white to off-white powder which may contain lumps, pH 6.9 (1.5 mg/mL), pKa: Non-ionizable compound.

Look-alike placebo tablets are supplied in the same container/closure system. The placebo tablets contain lactose monohydrate, microcrystalline cellulose, magnesium stearate, and coating material (Opadry® II).

5.2 Treatment Regimen

Participants will receive dapagliflozin 10 mg by mouth once daily or matching placebo for 24 weeks.

5.3 Method for Assigning Subjects to Treatment Groups

Patients will be randomized 1:1 in a blinded **fashion** to dapagliflozin or placebo with blinding and randomization performed by the Mayo Clinic Research Pharmacy.

5.4 Preparation and Administration of Study Drug

The IMP will be provided in bulk from AstraZeneca, to be labeled by the sponsor with a study specific label. Separate instructions for preparation and handling of the IMP will be provided by AstraZeneca in a Handling instruction.

5.5 Subject Compliance Monitoring

Compliance will be monitored and encouraged through frequent telephone calls/videoconference visits throughout the course of the study.

Page 13 of 34

Principal Investigator: [name]

5.6 Prior and Concomitant Therapy

Participants' chronic medications will not be changed for the purposes of this study. They will continue taking their home medications as prescribed, including on procedure dates unless contraindicated as clinical standards. Data for baseline medication usage will be obtained.

5.7 Packaging

The oral dapagliflozin tablets (10 mg) or matching placebo will be provided in bulk by AstraZeneca, and then shipped to the Research pharmacy at the Mayo Clinic. Appearance of active drug and placebo will be identical.

5.8 Masking/Blinding of Study

Only research pharmacy staff will be aware of randomization scheme and all study personnel and subjects will remain blinded to the identity of study drug. Placebo and dapagliflozin tablets have an identical appearance assuring maintenance of the blind.

5.9 Receiving, Storage, Dispensing and Return

5.9.1 Receipt of Drug Supplies

The oral dapagliflozin tablets (10 mg) or matching placebo will be provided in bulk by AstraZeneca, and then shipped to the Research pharmacy at the Mayo Clinic. Appearance of active drug and placebo will be identical. It is important that the designated study staff counts and verifies that the shipment contains all the items noted in the shipping invoice. Any discrepancies, damaged or unusable study drug in a given shipment (active drug or placebo) will be documented in the study files. The sponsor-investigator must be notified immediately of any discrepancies, damaged or unusable products that are received.

5.9.2 Storage

The study drug will be securely stored as recommended according to the instructions on the label.

5.9.3 Dispensing of Study Drug

Study drug (12 week supply plus 10 days additional for unavoidable events) will be provided by research pharmacy following randomization. A second 12-week supply of study drug will be may be mailed to participants prior to the 12 week point in the trial schedule.

Regular study drug reconciliation will be performed to document drug assigned, drug dispensed, drug returns, and drug remaining. This reconciliation will be logged on the drug reconciliation form, and signed and dated by the study team.

5.9.4 Return or Destruction of Study Drug

Participants are instructed to return all used, partly used and unused trial product at the final on-site study visit. Returned trial product(s) (used, partly used or unused including empty packaging material) must be stored separately from the non-allocated trial

Page 14 of 34

Principal Investigator: [name]

product(s) until drug accountability has been reconciled. The investigators will keep track of all received, used, partly used and unused trial products.

6 Study Procedures

6.1 Visit 1

At Visit 1, subjects will provide written informed consent. Medications will be documented and history and physical exam performed. Routine blood tests including complete blood count, creatinine, blood urea nitrogen, sodium, potassium, aspartate aminotransferase, alanine aminotransferase, total, direct and indirect bilirubin, hsCRP, NTproBNP, and HgbA1c will be performed up to 7 days before catheterization, if the same labs are drawn for other clinical appointments, study may use those values to save the patient an extra blood draw in addition to pregnancy test for women of child bearing potential.

In the preparation area, an IV cannula will be inserted in a forearm vein for initiation of isotope infusion ([U-¹³C] palmitate) to quantify free fatty acid (FFA) uptake during the procedure, allowing for attainment of steady-state prior to transfer to the catheterization laboratory (~60 min). Isotope infusions will be continued until blood sampling studies have been completed.

In the laboratory, right heart catheterization with simultaneous limited echocardiography and expired gas analysis will then be performed at rest and during supine cycle ergometer exercise as per standard practice. Pressures are measured in the right atrium, right ventricle, pulmonary artery, pulmonary artery wedge position, and radial artery are measured at end expiration at rest and throughout each stage of exercise. Cardiac output is measured using the direct Fick method.

After resting hemodynamic assessments have been performed, a 6 Fr MPA catheter will be advanced from the right internal jugular vein to the coronary sinus (CS) under fluoroscopic guidance, with CS location confirmed by oximetry (O₂ saturation<45%). Blood samples from the radial artery and CS will be drawn in triplicate (3 ml each) and averaged to measure blood gases (trans-myocardial O₂ uptake and CO₂ release based upon the difference between artery and CS tensions) along with glucose, lactate, triglyceride, pyruvate, ketone, and FFA uptake (total FFA and [U-¹³C]palmitate – enrichment in arterial and CS blood)). Additional mandatory research blood samples will be drawn frozen and stored for future discovery analysis. Samples will come from the CS, vein and artery once at the beginning of the procedure for future research. Samples will be transferred in iced tubes, centrifuged at 4°C and stored at -80°C for analysis.

Following resting metabolic assessments, participants will exercise at 20W workload on a supine ergometer for 3 minutes with the CS catheter in place, after which time arterial and CS sampling will be repeated during exercise in the same manner as at rest. The MPA catheter is then removed from the CS and exercise hemodynamic measurements are obtained. After obtaining exercise hemodynamic data at the 20W workload, workload is

increased in 20 W stages (3 minutes each) to volitional exhaustion. Hemodynamics and arterial and mixed venous blood samples are obtained at each stage.

Following exercise, catheters are removed and the patient is observed in the recovery area as per standard clinical practice prior to discharge.

6.2 Visit 2

At a second visit, typically the following day from the invasive catheterization can occur the day before visit 1 to allow flexibility, but no later than one week later, the patient will undergo plasma volume and blood volume assessment using the radiolabeled iodinated albumin ($^{131}\text{I},\,5{-}25~\mu\text{Cu}$) indicator dilution technique (BVA-100 Blood Volume Analyzer, Daxor Corp, NY) as is used clinically at Mayo Clinic and as we have described. 16 Patients will also undergo a DEXA scan in the Mayo CRTU.

At this visit QOL will be assessed using the SF-36 Questionnaire. Participants will receive the first 12 week supply of study drug as allocated in the randomization, and review study procedures and preferences for remote visits throughout the study period.

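### Section 6.1 derives trans-myocardial O₂ uptake from gas tensions instead of contents, so the O₂ denominator of exploratory endpoint 3.5(1) does not track O₂ uptake

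*Combined protocol and SAP*

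**What the plan says.** Section 3.5 opens its list with "Secondary exploratory endpoints will include", and item 1 is "Trans-cardiac uptake of free fatty acids (FFA), glucose, and ketone bodies uptake relative to O₂, as determined using arterial and coronary sinus blood sampling". It names the sampling sites but gives no formula for O₂.

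Section 6.1 is the only place that says how the O₂ term is obtained: "trans-myocardial O₂ uptake and CO₂ release based upon the difference between artery and CS tensions". Section 6.4 makes Visits 3 and 4 repeat Visits 1 and 2, so the same rule applies before and after treatment, at rest and at 20 W.

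Three other places bear on the point.
- Section 6.1 also states "Cardiac output is measured using the direct Fick method", but for cardiac output only. It mentions coronary sinus oximetry only as a check of catheter position (saturation below 45%).
- The only stated source of haemoglobin is the routine blood count, which section 6.1 allows up to 7 days before catheterization.
- Section 1.1 proposes that the drug may act in part "through improvements in cardiac function and reduction in plasma volume", and secondary objective 4 in section 2 asks whether treatment "can reduce plasma volume assessed by labelled albumin indicator dilution technique".

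**The concern.** A tension is a partial pressure. Nearly all O₂ in blood is bound to haemoglobin, so the O₂ taken up per unit of blood is a difference in content: haemoglobin times the saturation difference, plus a small dissolved term. Only the dissolved term is proportional to tension.

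The tension difference therefore goes wrong in two ways. It responds strongly to arterial PO₂, where the dissociation curve is nearly flat and content barely changes. It responds weakly to coronary sinus PO₂, where the curve is steep and the extraction signal lies. It also ignores haemoglobin, although section 4.2 admits anyone at 9 g/dL or above with no upper limit.

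At stake is the interpretation of the substrate-to-O₂ ratios that inform secondary objective 1. CO₂ release is defined by the same phrase and needs the same correction.

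**Working it through.** **The plan's own figure.** The only design figure is 93% power for exercise wedge pressure (section 7.5: 18 per arm, difference 6 mmHg, SD 5 mmHg, alpha 0.05, taken as two-sided). The noncentral t calculation gives 93.8%, close to the stated value. It does not involve the O₂ term. The plan gives no figure for endpoint 3.5(1).

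**Formulas.** O₂ content (mL/dL) = 1.34 × Hb × S + 0.0031 × PO₂, with saturation from the Severinghaus curve, S = 1 / (23400 / (PO₂³ + 150 × PO₂) + 1).

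**Assumed inputs, not in the documents.** Hb 12.5 g/dL, arterial PO₂ 90 mmHg, coronary sinus PO₂ 22 mmHg, haematocrit 0.38, plasma volume fall 5-10%, red-cell mass unchanged.

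**Base case.**
- Arterial: S = 0.969, content = 1.34 × 12.5 × 0.969 + 0.0031 × 90 = 16.52.
- Coronary sinus: S = 0.373, content = 1.34 × 12.5 × 0.373 + 0.0031 × 22 = 6.32.
- Content difference 10.19 mL/dL; tension difference 90 - 22 = 68 mmHg.
- Dissolved part: 0.0031 × 68 = 0.21 mL/dL, about 2% of 10.19.

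**Changing one tension at a time.**

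| Change | Tension difference (mmHg) | Content difference (mL/dL) |
|---|---|---|
| Arterial PO₂ 90 to 75 | 68 to 53 (-22%) | 10.19 to 9.80 (-4%) |
| Coronary sinus PO₂ 22 to 25 | 68 to 65 (-4%) | 10.19 to 8.85 (-13%) |

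**Other assumptions** (1.36 mL/g, Hb 13 g/dL).
- Coronary sinus saturation 35%, arterial PO₂ 70 to 100 mmHg: tension difference 48.9 to 78.9 (+61%), content difference 10.55 to 11.34 (+7%).
- Arterial PO₂ 85 mmHg, coronary sinus saturation 45% to 25%: tension difference 60.1 to 67.7 (+13%), content difference 9.27 to 12.83 (+38%).

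**Haemoglobin.** At arterial PO₂ 85 mmHg and coronary sinus saturation 35%, the tension difference is 63.9 mmHg at any haemoglobin. With 1.34 mL/g, the content difference is 7.60 mL/dL at Hb 9 and 12.54 at Hb 15.

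**Haemoconcentration at constant true extraction** (base case).
- Haemoglobin multiplier: 1 / (0.38 + 0.62 × 0.95) = 1.032 for a 5% plasma volume fall; 1 / (0.38 + 0.62 × 0.90) = 1.066 for 10%.
- To keep the content difference at 10.19, coronary sinus PO₂ must rise to 22.7 or 23.4 mmHg. The tension difference becomes 67.3 or 66.6 mmHg: -1.0% or -2.0%.
- A ratio with this denominator is overstated by 68 / 67.3 - 1 = 1.0% or 68 / 66.6 - 1 = 2.1%.

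**Plasma fraction.** The same falls take haematocrit from 0.38 to 0.392 or 0.405, and 1 - haematocrit from 0.62 to 0.608 or 0.595: -2.0% or -4.1%. This matters if substrates are assayed in plasma while O₂ is expressed per volume of whole blood.

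**The case against.** The best defence is that the word is loose and contents were meant. It sits in a parenthesis within a sampling paragraph, direct Fick output already needs O₂ contents, blood gases are scheduled at Visits 1 and 3, and section 7.6 promises that derivations will be documented in the code. This is plausible. It does not cure the rule as written: no other section defines the denominator, and an analyst following section 6.1 would subtract partial pressures. If contents were meant, the correction is the same.

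The second defence is importance. The endpoint is labelled exploratory, and being listed first gives it no special rank. Section 6.1 also collects lactate, pyruvate and labelled palmitate enrichment, so secondary objective 1 does not rest on this ratio alone. Both points stand and limit the weight of the finding.

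Third, under 1:1 blinded randomization, ordinary variation in arterial PO₂ is mainly noise common to both arms. That stands too. The documents give no between-visit PO₂ variability and no SD for this endpoint, so the loss of precision cannot be quantified.

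A reader might also infer a substantial bias between arms from haemoconcentration on dapagliflozin, of 3-6%. That size comes from raising haemoglobin with both tensions held fixed, which builds in a true rise in extraction. With true extraction constant the artefact is about 1-2%. The documents also do not establish that plasma volume falls, or falls only on active drug: secondary objective 4 poses it as a question. Nor do they mention supplemental O₂, so larger distortions at high arterial PO₂ have no basis in the plan.

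**Conclusion.** The rule in section 6.1 is wrong as written. A tension difference does not track O₂ uptake, and this holds under both sets of assumed values. The consequence for endpoint 3.5(1) is mainly extra noise from arterial PO₂ and a damped response to real changes in extraction: -4% shown where the content falls 13% in the base case. In that case the assumed coronary sinus PO₂ of 25 mmHg corresponds to a saturation of about 45%, at the limit of the catheter-position check; the alternative set, between 25% and 45%, shows the same pattern.

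Haemoconcentration is a minor addition, about 1-2% on the assumed 5-10% plasma volume fall at haematocrit 0.38. It would inflate all the substrate-to-O₂ ratios together, so it would work against the hypothesis for fatty acids and in its favour for glucose.

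The primary endpoint, sample size and power are untouched. The percentages depend on assumed haemoglobin, PO₂ and haematocrit values, but the absence of a haemoglobin term does not.

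**What to change.** In section 6.1, replace tensions with contents. Define O₂ uptake as arterial minus coronary sinus O₂ content, computed from haemoglobin, measured saturation and PO₂ on the same paired samples. Define CO₂ release as coronary sinus minus arterial CO₂ content.

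In section 3.5(1), state that each substrate's arterial-coronary sinus difference is divided by the O₂ content difference in molar units, with both on the same blood basis. Say whether substrates are assayed in plasma or whole blood; if plasma, convert with a factor of 1 - haematocrit. Without that step, the correction could leave a 2-4% haemoconcentration error of its own. Apply the definition at rest and at 20 W, at Visits 1 and 3.

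The cost is wording in two sections and a formula in the derivation code. Haemoglobin and saturation must be recorded from the blood-gas samples already drawn, not from a blood count up to 7 days old. This assumes that the analyser in use reports both, which the site should confirm. No further blood draw should be needed.
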